power analysis to determine the needed sample size to analyze the primary hypothesis under Aim 2 while balancing Type I and Type II error rates. Three sources of information were considered: (1) Existing empirical work involving cognitive training among AUD populations has established medium to large effect sizes for cognitive outcomes (partial η^2 = .1, Rupp et al., 2012; Cohen's d = .42, .64, Goldstein et al., 2005; partial η^2 = .27. Houben et al., 2011a), (2) [name] observed an effect size of d = .66 for Global Cognition in her recently completed study among individuals with schizophrenia comparing a cognitive training intervention to a computer-game control condition (both of which will be employed in the proposed study); (3) The magnitude of change in neuropsychological test performance required to detect a clinically significant and meaningful effect (e.g., Temkin et al., 1999). Together, the described considerations led to a sample size recruitment estimate of 128 participants (64 training, 64 control) for Stage 2, that will allow for up to 30% attrition. Calculations are based on the most conservative test of group mean differences, a 2-tailed independent samples t-test. Accounting for 30% attrition, a final sample size of 90 will provide an estimated power of 80% to detect a medium effect (d = .60) of cognitive training at follow-up (that is also within the range of observed effect sizes in other cognitive training studies with AUD) at an alpha level of .05. Given that previous cognitive training studies in AUD samples have reported medium sized effects for alcohol outcomes (partial η^2 = .16; Houben et al., 2011a; partial η^2 = .12; Rupp et al., 2012; partial η^2 = .1; Eberl et al., 2013) and psychological well-being (partial η^2 = .12; Rupp et al., 2012), the proposed sample size should also be adequately powered to test Aim 2 secondary hypothesis b (alcohol, PTSD and quality of life outcomes).

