The normality and range of data distributions will be examined and appropriate data transformations will be made when necessary. The data will also be screened for violations of assumptions underlying the statistical tests described below and when necessary, models will appropriately account for factors that vary with time across the study (i.e., training adherence). To control for Type-1 error rates cognitive outcomes will be tested using a Global Cognition Score (see 2a.3.i. Measures). Through randomization, we anticipate that the groups will be comparable in terms of demographic characteristics, premorbid intelligence, cognitive impairment, Axis-1 disorders, treatment participation, prescription medication use, training adherence and AUD and PTSD symptom severity. If significant differences exist, as indicated by Chi Square and t-tests, we will statistically adjust for these effects via inclusion as covariates in the analyses. We will conduct both a per protocol analysis on subjects who complete a minimum of 30 hours of training, and an intent-to-treat analysis on all randomized subjects, and report any differences in retention rates between the two conditions. For all models, variation inflation factors and tolerance will be obtained to assess for collinearity concerns. To account for family wise error, alpha will be adjusted in all secondary and exploratory analyses.

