Stage 2, Aim 2 Hypotheses 1a - b. Participants who receive cognitive training as compared to those receiving a computer-game control training, will demonstrate at 6 month post-training follow-up: Aim 2 Hypothesis a (Primary): greater improvements in cognitive outcomes (Global Cognition Score); Hypothesis b (Secondary): reduced alcohol consumption (drinks per drinking day) and PTSD symptoms (PCL-M) and improved quality of life outcomes (DUQLS, IPF). In order to test these hypotheses, a series of 5 multiple linear regression tests will be conducted to assess the effect of condition on each primary outcome. Step 1 will include the baseline level of the primary outcome. Condition (intervention, control) will be entered on Step 2. Step 3 will include any necessary covariates (described above in *Planned Data Analyses*) to determine if effects still remain. From this model we will be able to estimate the covariate and baseline adjusted mean changes, and 95%CIs, in global cognition, alcohol use, PTSD and quality of life outcomes 6 months posttraining. Secondary analyses. Planned secondary analyses will mirror the above description for primary analyses. First, to follow-up the analysis with global cognitive functioning, we will explore the effects of cognitive training on targeted cognitive domains using individual Cognitive Domain Scores as outcomes. Second, although we expect gains observed in the cognitive training group to be sustained throughout the follow-up period (i.e., persistence of neuroplasticity based cognitive training benefits), we will determine whether the Global Cognition Score changed from post-training to follow-up. This statistical approach is more dismantled and therefore more specific, and offers several advantages over repeated measures ANCOVA.

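### Persistence of the training gain from week 6 to 6 months is addressed only by a test for change, at a stricter alpha of unstated size, with no loss margin and no rule for reading a non-significant result

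*Combined protocol and SAP*

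**What the plan says.** All of this is in section 2a.3.j, Planned Data Analysis.

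- **Expectation.** Under the secondary analyses for Stage 2 Aim 2: "we expect gains observed in the cognitive training group to be sustained throughout the follow-up period".
- **Analysis.** In the same sentence: "we will determine whether the Global Cognition Score changed from post-training to follow-up". The method is given only by reference: "Planned secondary analyses will mirror the above description for primary analyses". The primary analysis is a stepwise linear regression (baseline score, then condition, then any covariates), from which adjusted mean changes with 95% CIs are to be estimated.
- **Alpha.** "To account for family wise error, alpha will be adjusted in all secondary and exploratory analyses". No method, family of tests or resulting level is given.
- **Power.** The calculation covers the primary comparison. It rests on "a 2-tailed independent samples t-test" with 90 evaluable participants and d = .60 at follow-up, "at an alpha level of .05". Stage 2 recruits "128 participants (64 training, 64 control) for Stage 2, that will allow for up to 30% attrition". No power is stated for the persistence question.

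The plan does not say whether the change is assessed within the training arm, between arms or in the pooled sample. It names no margin or retained fraction, and does not say how a non-significant change will be interpreted.

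**The concern.** The expected answer is no loss, but the tool is a test whose null hypothesis is no change. Failing to reject that null then agrees with the expectation, whether the gain held or the data were too imprecise to show that it had not. Attrition and measurement noise push the same way.

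A multiplicity correction normally makes a favourable claim harder to reach. Here the favourable outcome is non-significance, so a smaller alpha makes it easier.

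Durability matters to this plan. Section 2a.3.a (fifth design consideration) discusses lasting benefit when choosing the training duration, and section 2a.3.k says the data will feed a larger trial. A report that gains lasted, resting on a null test, could carry forward a loss that the study had little chance of seeing.

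**Working it through.** **1. Reproduce the plan's figure.** Two-sample t-test, 45 per arm, d = 0.60, two-sided alpha .05. The noncentrality is 0.60 × √(45/2) = 2.85, and power is 80.4%, against 80% stated. For attrition, 128 × 0.70 = 89.6, or about 90. The plan's sample size reproduces.

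**2. Inputs for the persistence question.**
- 45 evaluable per arm, from the plan.
- True loss of 0.30 SD from week 6 to 6 months: an assumption. It would be half of a week-6 gain of 0.60 SD. The plan sets d = .60 at follow-up, so 0.60 at week 6 is also an assumption.
- Correlation r between the week-6 and 6-month scores: not in the documents. Range 0.5 to 0.9, with equal SDs.
- Alpha: .05 unadjusted, or .05/5 = .01, which is Bonferroni over the four Cognitive Domain Scores of section 2a.3.i plus this test. The family is an assumption, because the plan does not define it.

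**3. Formulas.** SD of change = √(2(1 − r)), in units of the score SD. Noncentrality between arms = (0.30 / SD of change) × √(45/2), df 88. Within the training arm = (0.30 / SD of change) × √45, df 44. The miss rate is 1 − power from the noncentral t.

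Example, r = 0.7: SD of change = √0.6 = 0.775, and 0.30/0.775 = 0.387. Between arms, 0.387 × 4.743 = 1.84, missed 56% at .05 and 78% at .01. Within the arm, 0.387 × 6.708 = 2.60, missed 28% and 53%.

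**4. Chance that a 0.30 SD loss is non-significant.**

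| Contrast, alpha | r = 0.5 | 0.7 | 0.8 | 0.9 |
|---|---|---|---|---|
| Between arms, .05 | 71% | 56% | 40% | 12% |
| Between arms, .05/5 | 88% | 78% | 64% | 29% |
| Within training arm, .05 | 50% | 28% | 12% | 1% |
| Within training arm, .05/5 | 74% | 53% | 31% | 4% |

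Table 1 prints five domain rows where section 2a.3.i speaks of four. Counting five (.05/6) gives 89/80/67/32% and 76/56/34/5%, which does not change the picture.

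**5. A larger loss.** With a 0.60 SD loss at alpha .05, the miss rate for r = 0.5/0.7/0.8 is 20/5/1% between arms and 2/0.1/0% within the arm.

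**6. What mirroring the primary model would estimate.** Suppose it means regressing the 6-month score on the week-6 score plus condition. With equal SDs, the condition coefficient is (6-month arm difference) − r × (week-6 arm difference).
- Gain halved from 0.60 to 0.30: 0.30 − 0.5 × 0.60 = 0.00 at r = 0.5, and 0.30 − 0.7 × 0.60 = −0.12 at r = 0.7.
- Gain fully kept: 0.60 − 0.5 × 0.60 = 0.30, and 0.60 − 0.7 × 0.60 = 0.18.

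The between-arm loss is 0.30 in the first case and 0 in the second. The coefficient equals neither, so this contrast does not answer the question.

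**7. Precision.** The half-width of an unadjusted 95% CI for the change, at r = 0.5/0.7/0.9, is 0.42/0.33/0.19 SD between arms and 0.30/0.23/0.13 SD within the arm.

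**The case against.** **The plan contains no rule that non-significance means persistence.** This stands. The sentence states an expectation and a check on it. A reader might infer that a missed loss would be reported as sustained benefit, but the text does not say so. It leaves that reading open and places the expectation beside the test.

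**Benefit at 6 months is the primary endpoint.** This also stands, so it would be wrong to say that durable benefit is examined only by a test for change. It limits the harm. If the arm difference fell from 0.60 to 0.30, the primary t-test would be significant only about 29% of the time, and a failed primary would undercut any claim of lasting gain. I simulated both tests in the same trial (unadjusted t-tests, 45 per arm). A significant 6-month benefit together with a missed loss occurs between arms in about 5% (r = 0.9) to 26% (r = 0.5) of trials at alpha .05, and 11% to 28% at .05/5. Within the arm the ranges are under 1% to 19%, and 2% to 25%. However, the primary compares arms at one time and cannot say what share of the week-6 gain was kept.

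**The mirrored model already yields 95% CIs.** True, but no bound is compared with any amount of loss, so the interval has no stated role in judging persistence.

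**The 0.30 SD loss is illustrative.** Agreed. It has no basis in the documents, and neither does r. The stronger reading, that the study would generally miss a loss of half the gain, is not supported: it depends on the contrast, r and alpha, none of which is fixed. If d = .60 is what remains at 6 months after half the gain is lost, the loss is 0.60 SD and would usually be detected.

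**Conclusion.** The concern holds in a limited form. A test for change cannot support an expectation of no loss. The plan gives no margin, no contrast and no reading rule, and its multiplicity adjustment works in the wrong direction for this one question. For a 0.30 SD loss and r from 0.5 to 0.8, the miss rate at alpha .05 is 40% to 71% between arms and 12% to 50% within the training arm. At .05/5 it is 64% to 88% and 31% to 74%. These figures rest on 45 evaluable per arm, equal SDs, change-score t-tests and an assumed Bonferroni family. At r = 0.9 within the arm, the loss would nearly always be found.

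The documents do not show that the sponsor intends to report a null result as persistence, and the primary 6-month comparison is unaffected. The analysis is secondary and unpowered, so this is a cheap improvement to consider.

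**What to change.** Amend the secondary-analysis paragraph of section 2a.3.j as follows.

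1. Name the contrast: change within the training arm, or the difference in change between arms. Do not use the condition coefficient from a regression of the 6-month score on the week-6 score as the measure of loss.
2. Report the week-6 to 6-month change in the Global Cognition Score with a two-sided 95% CI, and state that a non-significant change will not be reported as persistence.
3. Claim that gains were sustained only if the CI excludes a loss that the sponsor sets in advance and justifies. The 0.30 SD used above is only an example. Otherwise report persistence as inconclusive.
4. Exempt this analysis from the alpha adjustment, or apply the adjustment by widening the CI, so that it makes the claim harder and not easier.

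The cost is a few sentences, with no new data or participants. The downside is imprecision. With 45 per arm, no true loss and the example margin, the 95% CI rule would confirm persistence about 29/44/60% of the time between arms and 50/72/88% within the training arm, at r = 0.5/0.7/0.8. The result will therefore often be inconclusive, which is the correct report at this sample size.

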The fifth_design consideration involved the "dose" of cognitive training to be administered. Previous research in schizophrenia populations has demonstrated that a signal may be detected at 20 hours (Keefe et al., 2011) though prolonged benefits (i.e., enduring cortical changes) require longer training periods (e.g., 50-80 hours; [name] et al., 2012). Cognitive training studies among AUD populations have employed highly variable training durations (2-20 hours) and schedules (4 to 25 sessions) and this variability appears to be driven by the nature of the exercises and the number of cognitive processes targeted (Fals-Stewart & Lam, 2010; Goldstein et al., 2005; Houben et al., 2011a; Rupp et al., 2012; Schoenmakers et al., 2010). Based on the training durations and associated gains previously observed in AUD populations (e.g., Bates et al., 2013), as well as the number of domains to be targeted and the associated exercises we will employ, we chose 30 hours as an optimal dose of training in the current study. Thirty hours will permit us to deliver approximately 7.5 hours of training targeting each of the 4 general cognitive domains illustrated in Figure 1 above.

The sixth design consideration was not to power the Stage 2 sample size to test whether change in cognitive outcomes mediates the relation between cognitive training (vs. computer game control) and recovery outcomes. Based on the early stage of research development ("Stage 1b efficacy"), we decided that powering the sample size for tests of mediation is not feasible or within the scope of the proposed research.

The seventh and final design consideration involved the decision to include individuals with comorbid Axis-I disorders (except Psychotic Disorders and Schizophrenia). Importantly, because AUD and PTSD are highly comorbid disorders, findings from the proposed study would dramatically suffer from limited generalizability should individuals with comorbidities be excluded from participation. Instead, Axis-I disorders and non-alcohol SUD will be comprehensively assessed and if necessary, controlled for if randomization procedures do not evenly disperse participants with comorbidities across conditions.

2a.3.b. Study Settings

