Stage 2, Aim 2a Exploratory Hypothesis. Changes in global cognition will be significantly associated with decreases in alcohol consumption, PTSD symptom severity and increases in quality of life outcomes. Change scores will be computed for the Global Cognition Score, average drinks per drinking day, the PCL-M and the DUQLS and IPF, by computing the difference between follow-up and baseline. Four Pearson correlations will be performed to test associations between composite index change scores for Global Cognition and the 4 recovery outcomes. Exploratory Mediation and Moderation. We will explore potential mediators (i.e., training adherence and performance) and moderators (i.e., AUD and PTSD severity; Alcohol Use) of the effects of training condition on cognitive outcomes. The MacArthur approach to moderation and mediation analysis (Kraemer et al., 2008) will be employed. These analyses are considered exploratory

because, although the study is powered to detect main effects, we will have power to detect only very strong interaction and mediating effects.

2a.3.k. Timeline for Primary and Secondary Research Activities (See Table 3).

Primary Research Activities. During the start-up phase (months 1-3) of the proposed work, we will coordinate recruitment procedures with the outpatient SUD treatment program, finalize and purchase assessment and training tools and train study personal in the study protocol. A recruitment goal of 4 eligible participants per month was chosen based on prior experiences of the mentorship team who agreed that the goal was realistic and sufficient to meet study objectives, and to allow adequate time to conduct follow-up assessments. Recruitment for Stage 1 will start month 4 and last for 5 months. The weekly and post-training assessments for Stage 1 will be completed in month 9 and 3 month follow-ups will be completed in month 12. We will reserve time during months 13 and 14 to incorporate feedback from Stage 1 to refine the protocol and optimize feasibility for Stage 2. Stage 2 recruitment will begin at month 15 and will last until approximately month 46-47. Therefore, including start-up and Stage 1, all data should be collected by the *middle of year 5*.

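### The four cognition–recovery correlations carry no term for condition, so an arm effect on both variables can inflate them

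*Combined protocol and SAP*

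**What the plan says.** The paragraph on the Stage 2, Aim 2a exploratory hypothesis in section 2a.3.j (Planned Data Analysis) states the hypothesis as "Changes in global cognition will be significantly associated with decreases in alcohol consumption, PTSD symptom severity and increases in quality of life outcomes".

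The variables are raw differences: "Change scores will be computed for the Global Cognition Score, average drinks per drinking day, the PCL-M and the DUQLS and IPF", obtained "by computing the difference between follow-up and baseline". The test is then: "Four Pearson correlations will be performed to test associations between composite index change scores for Global Cognition and the 4 recovery outcomes". The paragraph names no condition term, no split by arm and no restriction to one arm.

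The regressions for Hypotheses a and b, in the preceding paragraph, do contain the arm: "Condition (intervention, control) will be entered on Step 2". They also enter the baseline value of the outcome.

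The exploratory mediation analysis concerns a different link. It reads "We will explore potential mediators (i.e., training adherence and performance"), and these act on cognitive outcomes. The sixth design consideration in section 2a.3.a records the decision "not to power the Stage 2 sample size to test whether change in cognitive outcomes mediates the relation" between training and recovery.

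**The concern.** Pooling is not stated in words. It follows from the count: four outcomes and four correlations leave room for one combined sample per outcome, whereas separate arms would need eight.

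A pooled correlation mixes two things. One is whether, within an arm, participants whose cognition improved more also recovered more. The other is the separation of the two arm means. If training raises cognition and, by any route, also reduces drinking or PTSD symptoms, the arm means separate on both variables. That alone produces a correlation, in the hypothesised direction. A positive result would then partly restate Hypotheses a and b instead of adding evidence that cognitive change and recovery go together.

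Nothing else in the plan removes this. The covariate rule in section 2a.3.j covers characteristics that differ between the groups despite randomization, not condition itself. The mediation analysis does not examine the step from cognition to recovery. These four correlations are therefore the only planned test that links cognitive change to the recovery outcomes, and a reader may well take them as support for the conceptual model in section 2a.1.

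**Working it through.** **Inputs**

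- Final Stage 2 sample of 90 at 1:1 allocation, so 45 per arm (Power Analysis; section 2a.3.g).
- Effect on cognition d = .60, two-sided test, "at an alpha level of .05" (Power Analysis).
- Effects on alcohol outcomes cited there: partial eta squared .10, .12 and .16. Psychological well-being is also given as .12. No effect size is cited for PTSD symptoms.
- Alpha is to be adjusted for family-wise error in exploratory analyses (section 2a.3.j), method not named. Bonferroni over four tests, .05/4 = .0125, is an assumption here.

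**The plan's own figure.** A two-sided t-test with 45 per arm and d = .60 has 80.4% power by the noncentral t distribution, which agrees with the stated 80%. The plan gives no figure for the correlations.

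**Step 1: convert the cited effects.** Treating them as two-group effects, d = 2√(η²/(1 − η²)):

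- .10 gives .667
- .12 gives .739
- .16 gives .873

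**Step 2: correlation induced by the arms.** Take unit within-arm variances, zero within-arm correlation and equal arms. The pooled covariance is then d₁d₂/4 and each pooled variance is 1 + d²/4, so

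r = (d₁d₂/4) / √[(1 + d₁²/4)(1 + d₂²/4)].

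With d₁ = .60 the first variance is 1.09. For d₂ = .667: r = .100 / √(1.09 × 1.111) = .091. The other values follow in the same way. Signs are dropped; for drinking and PTSD symptoms the hypothesised sign is negative.

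**Step 3: rejection rates.** Simulation with 40,000 trials of 45 + 45 and zero within-arm correlation. "Adjusted" means the partial correlation given condition.

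| Effect on recovery outcome | Pooled r | Rejects at .05 | Rejects at .0125 | Adjusted, at .05 | Adjusted, at .0125 |
|---|---|---|---|---|---|
| d = .667 (η² .10) | .091 | 13.8% | 4.9% | 5.0% | 1.2% |
| d = .739 (η² .12) | .099 | 15.3% | 5.7% | 4.9% | 1.3% |
| d = .873 (η² .16) | .115 | 19.2% | 7.9% | 5.1% | 1.3% |
| d = 0 | 0 | 4.9% | 1.3% | 5.0% | 1.3% |

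Nearly all the excess lies in the hypothesised direction. At η² = .16 about 19% of trials reject in that direction and about 0.1% in the other.

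**Step 4: sensitivity to what d = .60 refers to.** The plan states d = .60 at follow-up, not for change. If it describes follow-up scores with equal variances and no baseline difference, the effect on change is d/√(2(1 − ρ)), where ρ is the baseline-to-follow-up correlation. The plan gives no ρ. With d = .60 at follow-up on both variables:

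- ρ = .5: effect on change .60, r = .083
- ρ = .7: effect on change .775, r = .130
- ρ = .8: effect on change .949, r = .184, with about 42% rejection at .05

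**The case against.** The strongest defence is that the hypothesis claims only an association between changes. It does not say that the association holds within arms, nor that cognition causes recovery. A pooled correlation is a legitimate estimate of that marginal association, and if training works through cognition, the between-arm part is genuine. The analysis is labelled exploratory, and mediation was openly left unpowered. This stands in part. It is a reason to keep the pooled figure as a description. It does not make that figure a clean test of the link, because the same value can arise with no link within either arm, and the plan does not label it as a mixture.

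The effect sizes are also soft. The cited partial eta squared values come from studies whose designs the plan does not give, so the conversion is an assumption. That limits the precision of the size, not the mechanism.

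Three stronger readings are tempting and are not supported:

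- **That the correlations will show an association from the arm effect alone.** This needs an arm effect on both variables. Even then, the induced r of about .1 lies below the critical value of .207 at n = 90 and alpha .05, so more than 80% of such trials would not reject.
- **That 14% to 19% is the plan's own error rate.** The plan adjusts alpha for exploratory tests. Under the assumed Bonferroni level the rate is about 5% to 8%, against 1.25% nominal. The adjustment lowers the rate but does not remove the bias.
- **That unadjusted change scores create a spurious correlation through regression to the mean.** The two changes come from different instruments. With no arm effect, unrelated true change and independent measurement errors, simulation gives a mean r of about 0 and about 5% rejection, even with baseline traits correlated at .5. Correlated errors across instruments would be needed, and nothing in the plan indicates them.

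**Conclusion.** The point holds as a conditional one. If training affects both cognition and a recovery outcome, the planned correlation for that outcome is inflated, by about .09 to .12 at the effect sizes that the plan uses or cites. False rejection then runs at roughly three to four times the nominal rate at .05 (13.8/5 = 2.8; 19.2/5 = 3.8), and four to six times at an assumed .0125 (4.9/1.25 = 3.9; 7.9/1.25 = 6.3).

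This rests on four assumptions: the arms are pooled, d = .60 applies to cognitive change, the eta squared values are two-group effects, and 90 participants are analysed. If d = .60 describes follow-up scores and the baseline-to-follow-up correlation exceeds .5, the inflation is larger. If either arm effect is zero, there is none.

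A reader might go further and infer that the trial's main conclusions are in doubt. They are not. The broad objective in section 2a.1 is tested by the baseline-adjusted regressions that include condition, and the primary test and its sample size are untouched. This is a cheap improvement to an exploratory analysis.

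**What to change.** For each of the four recovery outcomes, test and report the association between the two changes adjusted for condition, with a 95% confidence interval, and base the conclusion on it. Either a partial correlation or a regression of outcome change on cognition change with condition as covariate will do. The two baseline values may be added for consistency with the Hypothesis a and b regressions. The pooled Pearson r can stay as a descriptive figure, labelled as mixing between-arm and within-arm association.

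Replacing the correlations with regressions of follow-up outcome on follow-up cognition is not required; that is largely a matter of preference.

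The cost is a change of wording and one degree of freedom, or three with both baselines, out of about 90. No new data are needed. The real trade-off is that the adjusted estimate leaves out any between-arm association that truly runs through cognition, and the report should say so.
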